to a post-DVT activity regimen in children. I propose a validated, fitness tracker, the Fitbit, to improve adherence to a 16-week activity regimen in a pilot randomized controlled trial (RCT), in which 44 subjects with DVT will be assigned to the intervention group or to a comparison group. The primary outcomes will consist of a) feasibility indicators determined *a priori* (eligibility, consent, adherence, retention) and b) estimates of effect size associated with the prescribed activity regimen, by describing within-subject change in QoL and 'potential' biomarkers of PTS pre and post intervention in each group.

STUDY DESIGN (Figure 2)

The study design is that of a pilot RCT to test the feasibility of the proposed activity tracker to increase activity in children post DVT, against standard practice, which currently consists of providing education about PTS and instructions to 'be active'. I will use a validated activity tracker, the Fitbit and its data platform- the Fitabase.

METHODS

I. STUDY SETTING

All newly diagnosed patients with first, lower extremity DVT diagnosed at Children's Health System of Texas (CHST) or referred to the Hemostasis Thrombosis Center (HTC) at CHST who have completed 12 weeks (± 2 weeks) of anticoagulation therapy, will be approached for recruitment.

II. ELIGIBILITY CRITERIA

Parents must provide written, informed consent before any study procedures occur.

INCLUSION CRITERIA	RATIONALE
1. Age 7-21 years	VTE is seen across all age groups
2. A radiologically confirmed, acute, proximal (iliofemoral and femoropopliteal) first lower extremity DVT and/or confirmed,	Population with proximal DVT and/or PE deemed to be at highest risk of PTS

acute pulmonary embolism (unilateral or bilateral)	
3. 12 weeks (± 2 weeks) after starting anticoagulation	To mitigate the small theoretical risk of clot dislodgement with activity soon after DVT diagnosis
4. Out-patient ambulatory status	Protocol involves increasing activity

EXCLUSION CRITERIA	
1. Contraindication to increasing activity such as patients with juvenile arthritis, poor balance, congestive heart failure etc.	Protocol involves increasing activity

III. STUDY PROTOCOL

The study has 3-4 planned visits, which will coincide with the standard of care visits.

Screening

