- b. Subjects who need to continue long term prophylactic anticoagulation will still be eligible and will be included at discretion of their attending hematologist.
- c. The activity tracker, the Fitbit, is made up of a flexible durable material used in many sports watches (and one that does not contain latex) with a surgical grade stainless steel clasp and contains traces of nickel. It is meant to be worn day and night on the wrist. Because there's a possibility of skin irritation and allergies with any type of jewelry, all participants in this study will be warned and care and wearing tips will be provided. They will be monitored for any skin problems during the clinic visits and a treatment plan will be made in collaboration with their primary pediatrician should any skin irritation develop. I will ask to be notified immediately of any such occurrence at home and will then contact the participant or the family to assess

their clinical condition and make a treatment plan based on the severity of the skin condition.

VII. OUTCOMES AND POWER CALCULATIONS

Primary Outcomes will be 1) **feasibility indicators (Table 2)** measured throughout trial. The level of adherence in the intervention group will be calculated as the proportion meeting the weekly steps/day goal during the 'active' 8-week period of the total 16 weeks of intervention as determined by the Fitabase data platform output, and 2) **change in clinical outcomes**

such as PTS biomarkers at baseline and Visit 2, and QoL (at all visits). Secondary outcome: I will assess for PTS with validated scales at the 6 and 9 month follow-up visit as is standard of care.

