Analyses: The objectives of this trial are to assess the feasibility of the design and to measure the effect size of the intervention. All analyses will therefore be descriptive and will be performed once, at the end of the trial. Means and standard deviations, or when appropriate, medians and semi-inter-quartile ranges will be used to describe demographic and clinical characteristics. Reasons for non-eligibility, lack of consent, dropout and lack of compliance will be documented. For feasibility indicators, we (study investigators and [name]-biostatistician) will describe rate of eligibility (proportion of subjects screened who fully meet trial eligibility criteria to participate in the trial), rate of consent (the proportion of eligible subjects who consent to participate) and rate of loss to follow-up (proportion of randomized subjects who drop out of the trial, in total, and by allocated intervention). We will also describe the level of compliance in the intervention group, calculated as the ratio of who complied with the activity prescription to the number given the prescription. We will consider the trial *successful* if the following criteria are met: rate of eligibility $\geq 30\%$, rate of consent $\geq 30\%$, rate of loss of follow-up $<20\%$, level of compliance $\geq 60\%$ and proportion of subjects who complete the trial $\geq 80\%$. For the clinical outcomes (including the secondary outcomes), we will describe change (means and standard deviations) in the intervention and control groups, from baseline to 6 month, in the QoL scores and PTS biomarkers. Each change score will be interpreted for clinical significance and common responses counted for frequency of occurrence. The impact of the activity

Table 2: Feasibility Indicators

Proportion of screened subjects who meet eligibility criteria: $\geq 30\%$

Proportion of screened subjects who provide consent: $\geq 30\%$

Level of adherence in the intervention arm: $\geq 60\%$

Proportion of subjects who complete the trial: $\geq 80\%$

tracker to promote continued physical activity in the last 2 weeks of the 12-week period would be explored. We will also assess the impact of covariates such as age, sex, BMI, baseline activity, intensity of activity over and above the activity prescription, on change scores.

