Clinical information will be collected from each patient's electronic medical record at all visits while on study. This information will include the following: name, gender, race, ethnicity, date of birth, current medications, social history, patient medical and hospitalization history; family history, physical exam and laboratory results. Additional information to be collected from self reported diaries include adherence data and adverse reaction data. Returned diaries will be maintained in a research binder, while medical history, lab results, and medications will be recorded in the electronic medical record and then on electronic Case Report Forms (eCRF). Contact phone numbers for parents and relatives will be collected for the interim visit phone calls.

b. DATA MANAGEMENT

The eCRF will be housed in UT Southwestern REDCap. REDCap is a self-managed, secure, web-based data support system. The data is backed up offsite nightly and hosted in a secure environment maintained by Information Resources. This password protected study database will include a subject's personal identifiers and all Protected Health Information (PHI) such as medical history. All personnel who will be accessing the data will be trained in REDCap and have individual user ID and passwords. Subjects will have a study ID number that will be utilized in lieu of personally identifiable information for all research data provided to statisticians.

c. STATISTICAL ANALYSES

The following will be calculated: the proportion of screened patients who fully met trial eligibility criteria, the proportion of eligible patients who consented to participate, the proportion in the physical activity/ Fitbit group who adhered to prescribed activity, and the proportion of randomized patients who completed the trial (in total, and by allocated intervention). The feasibility outcomes will be reported descriptively

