using mean (standard deviations [SD]) for continuous outcomes, and raw counts (%) for categorical outcomes are reported. For the clinical end points, using an intent-to-treat analysis that includes all participants with data at baseline and 6 months (end of the intervention period), within-patient change from baseline (diagnosis or pre-VTE levels) to 6 months (mean, SD) in the physical activity will be compared to standard care in the following measures: D-dimer, FVIII, CRP, thrombin generation assay parameters of endogenous thrombin potential and peak thrombin, fibrinolysis on thromboelastography, QoL (total and physical), selfreported physical activity levels, and PTS (change from 6 to 9 months). This will be averaged for each group, and within-group differences will be compared between the standard care and physical activity groups using a t test. ECS use will be descriptively described but not included in a formal analysis.

ETHICS AND DISSEMINATION

I. RESEARCH ETHICS APPROVAL

This protocol and template informed consent forms will be reviewed and approved UT Southwestern IRB with respect to scientific content and compliance with applicable research and human subjects regulations. Subsequent to initial review and approval, the investigators will submit progress reports to the IRB at least annually and at study closure.

II. PROTOCOL AMMENDMENTS

Any modifications to the protocol, which impact the conduct of the study, or potential risk/benefit of the participants, will require a formal amendment to the protocol with IRB approval.

III. CONSENT OR ASSENT

Informed consent will be obtained after information has been provided to patients' families along with a discussion of the risks and benefits along with opportunity for questions. Consent forms will be provided for all parents involved in the trial.

IV. CONFIDENTIALITY

Records of each patient's participation in this study, including the original informed consent document, will be kept in a locked file cabinet in the Center for Cancer and Blood Disorders at Children's Medical Center. Access to local

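### The 30% consent threshold is set on screened subjects in Table 2 but on eligible subjects in the success rule, so the same counts can miss one and meet the other

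*Combined protocol and SAP*

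**What the plan says.** The Primary Aim lists the feasibility indicators fixed in advance as "eligibility, consent, adherence, retention", so consent appears once. Section VII (Outcomes and Power Calculations) makes "feasibility indicators (Table 2" the first primary outcome.

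The consent indicator is then given in three places:

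- **Table 2, Section VII:** "Proportion of screened subjects who provide consent", at least 30%. The denominator is everyone screened.
- **Analyses text, Section VII:** "rate of consent (the proportion of eligible subjects who consent to participate". The denominator is the eligible. The same paragraph calls the trial successful "if the following criteria are met: rate of eligibility" and the other listed rates reach their limits, including a consent rate of at least 30%.
- **Section II.c (Statistical Analyses):** "the proportion of eligible patients who consented to participate". The denominator is again the eligible; no threshold is restated.

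The eligibility indicator has no such split. Table 2 gives it as "Proportion of screened subjects who meet eligibility criteria", at least 30%, and both text passages also divide by those screened.

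**The concern.** One indicator carries one threshold, 30%, on two denominators. These cannot be two separate indicators: the Primary Aim names consent once, and its four items match the four rows of Table 2.

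Consent is among the criteria by which the pilot is to be judged, and the plan says a pilot is needed to establish feasibility before a definitive trial. If the result falls between the two versions, a reader working from Table 2 and a reader working from the success rule reach opposite conclusions on consent. The choice of denominator would then be made with the data in view.

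**Working it through.** **Inputs from the documents.** Eligibility threshold 30% of screened (Table 2 and Analyses text). Consent threshold 30% of screened (Table 2) or 30% of eligible (Analyses text). Planned size 44 (Sample size calculation). The 30% is a chosen criterion, so there is no computed figure in the plan to reproduce.

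**Assumptions.** Only eligible subjects are counted as consenting. The screened and eligible counts below are illustrative, because the documents give none.

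**Relation between the two versions.** Let e = eligible / screened and c = consenting / eligible.

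- Text rate = c.
- Table 2 rate = consenting / screened = e × c.

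Since e is at most 1, the Table 2 rate can never exceed the text rate. They agree only when e = 1 (or nobody consents).

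**Consent among the eligible needed to satisfy Table 2: c = 0.30 / e.**

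| Eligibility rate e | c needed for Table 2 | c needed for the text | Table 2 rate when c = 30% |
|---|---|---|---|
| 30% | 100% | 30% | 9% |
| 40% | 75% | 30% | 12% |
| 50% | 60% | 30% | 15% |
| 60% | 50% | 30% | 18% |
| 80% | 37.5% | 30% | 24% |
| 100% | 30% | 30% | 30% |

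**At both text thresholds exactly.** 200 screened, 60 eligible (60/200 = 30%), 18 consenting (18/60 = 30%). Both text criteria are met. The Table 2 rate is 18/200 = 9%, and Table 2 would need 0.30 × 200 = 60 consenting.

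**Away from that corner.** 200 screened, 100 eligible (50%), 44 consenting. Text: 44/100 = 44%, met. Table 2: 44/200 = 22%, missed.

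**At the planned size, taking 44 as the number consenting.** 44 / 0.30 = 146.7.

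- The text criterion is met with up to 146 eligible. At 30% eligibility that allows up to 486 screened (146 / 0.30 = 486.7).
- The Table 2 criterion is met only with up to 146 screened.

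**Direction of the conflict.** Under the assumption, consenting ≤ eligible ≤ screened. Meeting Table 2 therefore always meets the text, and any conflict takes the form of text met, Table 2 missed. Enumerating all whole-number counts up to 300 screened found no exception.

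**Effect on the eligibility row.** Under the same assumption, if at least 30% of those screened consent, at least 30% of them are eligible. Read literally, Table 2 leaves its own eligibility threshold with nothing to do, which also suggests a wording slip in the consent row.

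**The case against.** The strongest reply is that the success verdict has only one answer. The sentence declaring success uses a term that its own paragraph defines over eligible subjects, and it does not refer to Table 2. The Statistical Analyses section agrees. On this view Table 2 is a slip that the text overrides. That is fair for the success sentence taken alone. It does not settle the primary outcome, which Section VII ties by name to Table 2.

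A second reply concerns the order of events. The Screening text lets consent be taken in hospital, and the footnote to Table 1 allows it from diagnosis up to Visit 1. Two inclusion criteria are about 12 weeks since the start of anticoagulation and outpatient ambulatory status, so some subjects could consent before they can be confirmed eligible. Study Setting points the other way, since it approaches patients who have completed about 12 weeks of treatment. If consent can come first, the conflict can reverse. Suppose 200 are screened, 50 are eligible, and 66 consent, of whom 14 are eligible. Table 2 gives 66/200 = 33% (met), the text gives 14/50 = 28% (missed), and eligibility is 50/200 = 25% (missed). The direction, the table of required rates and the redundancy of the eligibility row therefore hold only under the stated assumption. The difference in denominators does not depend on it.

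Third, the redundancy argument is only supporting evidence. The success rule already contains an overlapping pair, loss to follow-up below 20% and completion of at least 80%. The agreement of the two text passages against one table row is the better evidence of a slip.

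Finally, the 100% and 9% figures belong to the extreme of exactly 30% eligibility. The documents do not define the screened pool; if it is already narrowed to likely candidates, eligibility may be much higher and the gap smaller. The analyses are descriptive, and the plan undertakes that "raw counts (%) for categorical outcomes are reported", so a reader could recover both rates. All of this stands and limits the weight of the point. Reported counts still do not show which threshold was set in advance.

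**Conclusion.** The inconsistency is real. A pre-set threshold for a primary-outcome indicator is stated on two denominators, and the plan does not reconcile them. If only eligible subjects are counted as consenting, Table 2 is stricter by the factor 1/e: it requires 100% consent among the eligible at 30% eligibility, 60% at 50% and 37.5% at 80%, against 30% in the text. How likely the versions are to disagree in practice cannot be said, because no expected eligibility rate is given. The likeliest explanation is one mis-worded row. Treatment, randomisation, data collection and sample size are unaffected. It should be fixed because it changes whether a stated feasibility criterion is met, but it is a small correction.

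**What to change.** In the consent row of Table 2, replace screened with eligible and keep the 30% threshold. The row then matches the definition behind the success rule and the denominator in the Statistical Analyses section.

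It would help to add one sentence saying whether a subject who consents before eligibility is confirmed counts in the numerator, since the change of word alone leaves that open.

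The cost is one word in one table row, plus the optional sentence. No procedure, data item or sample size changes.

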The parents/legal guardians will be given an explanation about the study and informed consent and/or assent will be obtained. This may occur in the inpatient or the outpatient setting. Demographic information and relevant medical history, including results of scans and thrombophilia testing will be collected. All medications, including anticoagulant medication received for the thrombotic event will be recorded.

a. Baseline Assessments (collected as SOC (standard of care)):

i. History and Physical Examination:

1. Detailed history regarding medical disorders predisposing to thrombosis and potential triggers (birth control pills, recent travel or surgery or immobility) and predispositions (thrombophilia, obesity etc.) will be collected.
2. Review of existing medical records recorded on Children's Medical Center electronic medical record to review past medical, family and social history will be performed.
3. Comprehensive physical exam (PE) consisting of vital signs, general appearance, head, eyes,

ears, nose, throat (HEENT), cardio-respiratory, abdominal, extremities and skin will be performed at each visit as per standard of care.

- ii. Laboratory:
 - 1. Complete blood count (CBC), reticulocyte count, baseline coagulation studies, and a comprehensive thrombophilia panel performed as SOC will be recorded.
- iii. Treatment:
 - 1. Information on anticoagulant therapy (medication of choice, intensity of anticoagulation, planned duration of therapy) prescribed as per the treating physician will be collected for subjects who meet eligibility criteria and whose parents provide written informed consent
- iv. Radiological:
 - 1. All information related to site, extent and venous segments involved of the thrombotic venous segment at the time of diagnosis, and at completion of therapy will be collected. Information on reflux assessment at the time of end of therapy ultrasound will also be collected.
- v. Assessment of **Post-thrombotic syndrome (PTS)**: All subjects will be assessed with standardized, validated outcome assessment tools: the Manco-Johnson Instrument and the modified Villalta scale starting at 6 months post diagnosis of DVT as per standard of care. See appendix 1 for these scales.

b. Study Interventions:

i. Study procedures/Randomization:

Eligible, consenting subjects will be individually randomized via a web-based program to the Fitbit arm or the control arm (1:1 allocation ratio).

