- 1. **Intervention (Fitbit) arm.** The intervention arm will wear a Fitbit for a 16-week period (**Figure 2**). **General Principles of an aerobic activity regimen:**

As the principal muscles affected by PTS are the lower limb muscles, we have opted to use a walking-jogging program to capture steps/day by the Fitbit. This will target all potentially affected muscles (quadriceps, hamstrings and gastrocnemius/soleus). If preferred by the subject, other weight bearing exercises could replace the walk/jog, for example, dancing or team sports such as basketball or volleyball. Because of the unfamiliarity with activity trackers, subjects will be provided with hands-on training to promote successful use of the Fitbit and Fitabase.

a. Schedule and procedures (Table 1): After consent (baseline visit), subjects in this arm will receive a standardized 15-20 minute education session on PTS (what constitutes PTS, why patients get it, how to manage it) and enhanced activity after DVT. Subjects will be asked to wear the Fitbit for a period of four weeks to establish baseline or 'habitual' activity. Using steps/day data received at the end of four weeks, we will determine an individualized activity prescription of 'target steps/day', corresponding to a 25% increase above the baseline.

Table 1	Visit 1	Visit 2	Visit 3
	12 wks post DVT Dx (\pm 2 weeks)	16 wks after Visit 1 (\pm 4 weeks)	8 wks after Visit 2 (\pm 4 weeks)
	SOC Visit	SOC Visit	SOC Visit (Exit Visit)
ALL SUBJECTS			
Informed Consent	X*		
Full Medical History and Exam	X	X	
Biomarker Testing [^]	X\$	X	X
FXIII, D-dimer, CRP	X	X	X ^{^^}
QOL forms	X	X	X
PTS Assessment		X	X
ECS and Log	X	X~	X~
Activity Logs/ Questionnaire	X	X	X
Medication Log***	X	X	X

Phone Calls (monthly)	X	X	
Formal Education Session	X		
Honoraria**	X	X	X
SUBJECTS IN FITBIT ARM			
Hands on Fitbit Training	X		
Steps/Day Data (weekly)	X	X	X
Phone Calls (weekly)	X	X	
Return Fitbit			X

*Informed consent can occur any time after DVT diagnosis until Visit 1; ^Biomarker testing includes: D-Dimer, FVIII, Thrombin generation, markers of fibrinolysis; \$Biomarker testing at Visit 1 may be combined with other SOC labs for those still on anticoagulation at this time; ~ only ECS logs; ** \$25 at Visit 1 and 2, and \$50 at Visit 3; ***Medication logs only for participants on Rivaroxaban or Xarelto; ^^Factor VIII, D-dimer, and CRP can be completed as research procedures at Visit 3 for participant's whose values were within normal range at Visit 2.

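### The t test on coagulation and fibrinolysis biomarker change ignores anticoagulation status, which is mixed at Visit 1 and already recorded; the cost is precision, not validity

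*Combined protocol and SAP*

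**What the plan says.** Biomarker change between baseline and Visit 2 is one of the primary outcomes (section VII, Outcomes and Power Calculations). Under Statistical Analyses, change is averaged per arm and "within-group differences will be compared between the standard care and physical activity groups using a t test". That section proposes no model and no adjustment.

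Covariates appear once, in the Analyses paragraph of section VII: "We will also assess the impact of covariates such as age, sex, BMI, baseline activity", followed by intensity of activity beyond what was prescribed, all in relation to the change scores. Anticoagulation is not in the list. Randomisation is individual and 1:1, with no stratification described.

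Four other places bear on anticoagulation:

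- Study Setting: patients are approached "who have completed 12 weeks (± 2 weeks) of anticoagulation therapy".
- Table 1 footnote: "Biomarker testing at Visit 1 may be combined with other SOC labs for those still on anticoagulation at this time". Some subjects are therefore treated at the first draw and, by implication, others are not.
- Concomitant Care, item b: "Subjects who need to continue long term prophylactic anticoagulation will still be eligible".
- Study Protocol, baseline item iii (Treatment): "Information on anticoagulant therapy (medication of choice, intensity of anticoagulation, planned duration of therapy" are collected. Current medications are also taken from the record at every visit (Data Collection Methods), and anti-Xa, INR or a medication log is kept depending on the drug (study assessments, item 6).

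**The concern.** The study assessments section itself classes D-dimer, FVIII and thrombin generation as markers of coagulation activation, and TEG among the markers of fibrinolysis. Anticoagulants act on coagulation. Enrolment falls at about 12 weeks of treatment and Visit 2 comes 16 weeks later (± 4). Between the two draws some subjects may stop, while others continue or were already off. Change in these markers can therefore reflect a change of treatment status as well as activity, and the planned test leaves that variation in the error term.

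The omission does not look deliberate. For compression stockings the plan says outright that use will be described and kept out of the formal analysis; it says nothing comparable for anticoagulation. At stake is the precision of an effect-size estimate that is a stated objective and may inform later studies.

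**Working it through.** **The plan's own figure.** The only power figure is 71%, for PTS risk of 26% versus 10% at p<0.2. It reproduces as 70.9% with 22 per arm, one-sided 0.2 and the pooled normal approximation. It concerns PTS and does not depend on this point. The documents give no effect size, SD or power for biomarker change, so what follows uses assumed values.

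**Inputs.** From the sample size paragraph: 20 evaluable per arm. Assumed: p, the share who stop between the draws, 30-70%; d, the shift in change score caused by stopping, 0.5-1.5 in units of the SD among subjects with the same treatment pattern.

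**Step 1: variance left in the error.** Factor = 1 + p(1-p)d².

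| p | d | Factor |
|---|---|---|
| 0.3 or 0.7 | 0.5 | 1 + 0.21 × 0.25 = 1.05 |
| 0.5 | 0.5 | 1 + 0.25 × 0.25 = 1.06 |
| 0.5 | 1.0 | 1 + 0.25 × 1 = 1.25 |
| 0.3 or 0.7 | 1.5 | 1 + 0.21 × 2.25 = 1.47 |
| 0.5 | 1.5 | 1 + 0.25 × 2.25 = 1.56 |

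The standard error grows by the square root of the factor: 1.12 in the central case (√1.25) and 1.25 at the top (√1.5625).

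**Step 2: chance imbalance is part of this, not an addition.** At p = 0.5 the SD of the between-arm difference in the share stopping is √(2 × 0.25/20) = 0.158, which at d = 1 moves the estimate by 0.158 SD. The standard error without the anticoagulation component is √(2/20) = 0.316; with it, √(2 × 1.25/20) = 0.354. Since 0.316² + 0.158² = 0.100 + 0.025 = 0.125 = 0.354², the imbalance term is exactly the extra variance of Step 1.

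**Step 3: how often a visible imbalance occurs.** With two independent binomial counts of 20, the chance that the arms differ by at least 20 percentage points is 27% at p = 0.5 and 20% at p = 0.25 or 0.75. An imbalance of 20 points moves that trial's estimate by 0.2d, that is 0.1-0.3 SD for d = 0.5-1.5.

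**Step 4: power, for scale.** For an assumed true effect of 0.8 within-pattern SD, 20 per arm, two-sided 0.05 and the noncentral t, power is 69% if the pattern is fully accounted for (ignoring the degree of freedom spent). Unadjusted, for p between 0.25 and 0.75, it is 67% at d = 0.5, 60-62% at d = 1 and 51-54% at d = 1.5.

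**Step 5: what adjustment can recover.** Steps 1 and 4 treat actual stopping as known. A baseline covariate captures planned stopping, so it removes only the part of the extra variance that the plan for treatment predicts. The figures are upper limits on the gain.

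**The case against.** The strongest reply is that little depends on this. The covariate list is open-ended, so anticoagulation is not excluded. All analyses are called descriptive, the success criteria are feasibility thresholds only, and the sample size paragraph promises caution because of the small numbers. All of that is correct, and it limits the weight of the point. It does not remove it: measuring the effect size is an objective, a between-arm test is specified, and a covariate chosen after the data are seen is worth less than one named beforehand.

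A reader might go further and infer that the t test is biased, or that it will produce false differences. The documents do not support that. Allocation is randomised, so anticoagulation is balanced in expectation, and the t test's standard error already contains the variation it causes. The false-positive rate is not raised.

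A reader might also extend the point to every biomarker. The argument covers the markers that the protocol ties to coagulation and fibrinolysis. It does not cover CRP, which the protocol lists as a marker of inflammation.

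Finally, the size is assumed throughout. The two-group model is also simpler than the documents, which allow at least three patterns: off at Visit 1, stopping between visits, and continuing. If nearly everyone is already off, or nearly everyone continues, few stop between draws and the loss is small.

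**Conclusion.** The point holds as one about precision. The planned comparison for a primary outcome leaves out a baseline variable that the trial already collects and that plausibly drives these markers. Under the assumed ranges, change-score variance is about 5-56% larger than it need be, with 25% as the central value. At the low end the loss is negligible; at the high end it costs about 15-18 points of power for an effect of 0.8 SD (69% against 51-54%). The feasibility conclusions are untouched.

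One premise needs settling by the authors. The Statistical Analyses section ties baseline to diagnosis or to levels before the clot, whereas Table 1 has the first biomarker draw at Visit 1. The working above takes Visit 1 as baseline. The two passages must be reconciled, because they determine which anticoagulation status applies.

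**What to change.** 1. In Statistical Analyses, replace the t test for D-dimer, FVIII, thrombin generation and TEG fibrinolysis with a linear model for the change score. Include arm and prespecified baseline anticoagulation: on or off at the Visit 1 draw and, if on, planned to stop before Visit 2 or not. Take both from the baseline record, not from what happened later.
2. Name this covariate in the Analyses paragraph of section VII.
3. Tabulate actual anticoagulation status at each visit by arm, so that any imbalance is visible.
4. If an analysis restricted to subjects with the same status at both draws is wanted, label it exploratory and non-randomised, or leave it out. It selects on status at Visit 2, which is observed after randomisation, and with half stopping it would keep about 20 × 0.5 = 10 per arm.

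The cost is a short edit in two places and one or two of the t test's 38 degrees of freedom (2 × 20 - 2). No new data are needed and nothing in patient care changes.
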